ORI IRB# 00000278

Protocol Version 1/15/2018

Official Title: Responsive e-Health Intervention for Perinatal Depression in Healthcare Settings

Principal Investigators: [name].

Oregon Research Behavior Interventions Strategies, dba Influents Innovations

Award No. MH109191

Final Version Dated: 1/15/2018

STUDY PROTOCOL

Participant Recruitment, Enrollment, and Randomization

Depressed perinatal women were recruited from NorthShore University HealthSystem – a Chicago-based healthcare system that has 6 hospitals, over 3,000 primary care physicians and specialists. Study recruitment followed a step-wise process embedded within NorthShore’s Perinatal Depression Program (PDP) beginning with universal screening approximately 26-28 weeks into pregnancy and 6 weeks postpartum using the Edinburgh Postnatal Depression Scale (EPDS; score > 12). PDP social workers called women with positive depression screens in order to tailor recommended treatment, including community mental health referrals. Based on their clinical judgment and knowledge of the eligibility characteristics of women to be considered for Northshore’s Mom Mood Study, social workers also provided a brief description of the study in the call.

Interested women were referred to the study coordinator who provided a more complete study description and determined final eligibility using the following criteria: <1 year postpartum, ≥18 years of age, no active suicidal ideation, access to broadband internet via computer (desktop/laptop, tablet or smartphone), and English language proficiency. Women with affirmative answers to question of EPDS self-harm were included in the study if social work deemed them low-risk for suicide. Patients with active suicidal ideation were excluded.

REDCap (Version 8.10.5) was used to accomplish all subsequent onboarding steps, including informed consent, randomization to group, online assessments, tailored emails, and data management. Eligible women remained blind regarding their allocation to treatment group until being informed by the study coordinator who used REDCap’s randomized tool blocked on perinatal status (pregnant or postpartum) and the two groups. Following randomization, the research team was not blind as to participant group.

Perinatal Depression Program (PDP)

NorthShore’s well-established PDP includes universal perinatal outpatient depression screening with both centralized scoring and a referral network of community mental health providers, a 24/7 crisis hotline to respond to urgent/emergent patient needs, and relevant curriculum for obstetricians and nurse midwives.

MomMoodBooster + Perinatal Depression Program (MMB2+PDP)

Women in the MMB2+PDP group could use MMB2 and the PDP. MMB2 recommends increasing pleasant activities to regain life balance, interrupting negative thoughts and increasing positive thoughts, seeking support from others, and tracking mood. MMB2 included videos, audios, animations, and editable lists in a browser-based Web app that responsively adapted to each user’s device (smartphone, tablet, laptop, and desktop). During the 12-week active treatment phase, each of the six MMB2 sessions becomes available sequentially according to a weekly schedule. Thereafter, users could continue visiting MMB2 for 7 additional months. The study coordinator enrolled women to MMB2 using the program’s administrative website. Each pregnant woman’s due date was used by MMB2 to ask the participant if they had delivered their baby in order to change from pregnant to postpartum program content. Two team outreach calls were made by a NorthShore team member not trained in mental health treatment. Call #1, 2-4 weeks following randomization, focused on resolving any difficulties signing into MMB2. Call #2, scheduled after the posttest, collected open-ended feedback about the program.

Measures and Assessments

Participant characteristics were assessed at baseline and outcomes were assessed at baseline and the 12-week posttest. Participants who completed all assessments received a \$100 e-gift card.

In terms of primary outcomes, the Patient Health Questionnaire (PHQ-9) used to assess the severity of depressive symptoms has been well-validated, found reliable and sensitive, and widely used with perinatal depressed women – including in our prior MMB research, and other studies in large healthcare systems. We used the Depression Anxiety Stress Scale (DASS-21) Anxiety scale to assess anxiety symptom severity because perinatal anxiety is commonly comorbid with depression and has been related to adverse perinatal outcomes.

For secondary outcomes, the DASS-21 stress scale was used to assess stress severity, the Behavioral Activation for Depression Scale (BADS-Short Form) to measure behavioral activation, the short-form version of the Automatic Thoughts Questionnaire (ATQ-SF) to measure negative thoughts associated with depression, and a measure of behavioral self-efficacy to assess use of MMB2 strategies to manage activities, positive/negative thinking, support, relaxation, and goal setting.

Additional measures included MMB2's continuous and unobtrusive tracking of each user's MMB2 visits, session visits (date, number, duration), and activities (e.g., number/duration of videos and animations viewed, personal list updates). In addition, women who visited MMB2 (confirmed by unobtrusive engagement metrics) were asked on the posttest to rate MMB2's usability and helpfulness, the helpfulness of team outreach calls, and whether they would recommend MMB2. Participants in both groups were asked whether they used other mood management products or programs while in the study.

STATISTICAL ANALYSIS PLAN

Preliminary analyses examined distributional properties of measures, baseline equivalency, and missing data. Intent-to-treat analyses of group effects were performed using fixed effects growth models fit (SAS PROC MIXED; Version 9.4) and estimated with maximum likelihood. Individual variability in outcomes from baseline to posttest were predicted by a two-level dummy coded group variable (coded 0 for PDP and 1 for MMB2+PDP), a time variable (coded in months elapsed between baseline and posttest), and a group \times time interaction. Effect sizes for the group \times time interaction are equivalent to Cohen's d. Moderation of group \times time effects for the primary depression outcome (PHQ-9) were evaluated by adding in separate models, the main effects of baseline perinatal status (pregnant/postpartum), the EPDS primary screen, baseline PHQ-9, and all two- and three-way higher order interactions with group and time.

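### Randomisation is blocked on perinatal status, but the main growth models omit it; if change differs by status, the standard error of group × time is overstated

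*Combined protocol and SAP*

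**What the plan says.** **Randomisation.** Under Participant Recruitment, Enrollment, and Randomization, the protocol says the coordinator used REDCap's "randomized tool blocked on perinatal status (pregnant or postpartum) and the two groups". Block size and the expected split between pregnant and postpartum women are not given.

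**Visits.** Under Measures and Assessments, "outcomes were assessed at baseline and the 12-week posttest", so each outcome has two time points. The primary outcomes are PHQ-9 and DASS-21 Anxiety. The secondary outcomes are DASS-21 Stress, BADS-SF, ATQ-SF and self-efficacy.

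**Main models.** The Statistical Analysis Plan says outcomes are "predicted by a two-level dummy coded group variable (coded 0 for PDP and 1 for MMB2+PDP), a time variable" in months, and the group × time product. No other term is listed. The treatment effect is the product term: effect sizes for the group × time "interaction are equivalent to Cohen's d".

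**Where status appears.** It appears only in the moderation analysis. The wording there is "effects for the primary depression outcome (PHQ-9) were evaluated by adding in separate models", and the terms added are "the main effects of baseline perinatal status (pregnant/postpartum), the EPDS primary screen, baseline PHQ-9", with their two- and three-way interactions with group and time.

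**The concern.** The trial balances the groups on perinatal status by design and then analyses the data as if it had not. Balancing on a factor that predicts the outcome reduces the true variability of the treatment estimate. A model that omits the factor does not see that reduction and reports a standard error that is too large.

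What matters here is whether status predicts *change*. A difference between pregnant and postpartum women that is the same at both visits drops out of group × time and does no harm. A difference in mean change does not drop out.

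Such a difference is plausible, though the documents do not show one. Pregnancy screening is at about 26-28 weeks and the posttest comes 12 weeks after baseline. A woman enrolled straight after that screen would be at about 38-40 weeks (26 + 12 to 28 + 12), around delivery, while postpartum women have already delivered. The sponsor also chose status both as the blocking factor and as a candidate moderator.

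The stake is precision: intervals wider than necessary and some lost power on two primary and four secondary outcomes. Bias and excess false positives are not at issue.

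**Working it through.** The plan states no sample size, alpha, power, stratum split or change by status, so it has no figure of its own to reproduce. The check shows a range instead.

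**Inputs**
- From the documents: a two-level blocking factor; two visits; a main model with group, time and group × time.
- Assumed: blocks within strata with 1:1 allocation; two-sided 5% alpha; 80% power for the analysis that includes status; share *p* of women in one stratum (0.5 or 0.3); difference *D* between strata in mean change, in within-stratum SDs of change (0, 0.2, 0.5, 0.8).

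**Formulas.** With two complete visits at common times, group × time is the between-group difference in mean change. For *n* women and within-stratum SD of change σ:
- true variance under stratified blocks: 4σ²/n
- variance reported when status is omitted: 4σ²[1 + p(1−p)D²]/n
- ratio of reported to true standard error: r = √[1 + p(1−p)D²]
- actual type I error: 2[1 − Φ(1.96r)]
- power: Φ(2.80 − 1.96r)
- interval width expressed as fewer women in the adjusted analysis: 1 − 1/r²

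**Example**, p = 0.5, D = 0.5: r = √(1 + 0.25 × 0.25) = √1.0625 = 1.031. Type I error = 2[1 − Φ(2.02)] = 4.3%. Power = Φ(0.78) = 78.3%. Fewer women = 1 − 1/1.0625 = 5.9%.

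| Split | D | SE overstated by | Type I error | Power | Interval width as fewer women |
|---|---|---|---|---|---|
| 50:50 | 0 | 0% | 5.0% | 80.0% | 0% |
| 50:50 | 0.2 | 0.5% | 4.9% | 79.7% | 1.0% |
| 50:50 | 0.5 | 3.1% | 4.3% | 78.3% | 5.9% |
| 50:50 | 0.8 | 7.7% | 3.5% | 75.5% | 13.8% |
| 30:70 | 0.2 | 0.4% | 4.9% | 79.8% | 0.8% |
| 30:70 | 0.5 | 2.6% | 4.4% | 78.5% | 5.0% |
| 30:70 | 0.8 | 6.5% | 3.7% | 76.2% | 11.8% |

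**Simulation** (200 women, 50:50 strata, 1:1 within strata, two complete visits, SD of change 1, 20,000 replicates)
- Shift of 0.5 or 1.0 SD equal at both visits: SE of group × time is 0.141 with or without status.
- Change difference of 0.5 SD: reported SE 0.146 against a sampling SD of 0.141; type I error 4.4%; power 77.9% without status and 79.7% with it.
- Change difference of 0.8 SD: reported SE 0.152 against 0.142; type I error 3.7%; power 75.1% without status and 80.0% with it.

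**Is blocking the cause?** In a separate simulation (200 women, change difference 1.0 SD, blocks of 4, 10,000 replicates), the reported SE without status was 0.158 against a sampling SD of 0.142. With unstratified allocation both were 0.158. The overstatement therefore comes from blocking on status and then leaving it out.

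**Which term is needed?** In a two-visit random-intercept model fitted by maximum likelihood (change difference 1.0 SD), the reported SE was 0.158 with no status term, 0.158 with a status main effect only, and 0.141 once status × time was added.

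**The case against.** **The PHQ-9 moderation model already contains status and status × time.** A status-averaged effect could be obtained from it as a linear contrast, and in simulation that contrast had an SE of 0.141, as good as the fix. This is true, but the plan specifies no such contrast. With status dummy coded, the model's own group × time coefficient is the effect in the reference stratum. It would also cover only one of six outcomes.

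**Maximum likelihood shrinks the standard error.** Dividing by n makes it about 0.5% smaller with 200 women (√(198/200) = 0.995). At a 0.2 SD difference this roughly cancels the overstatement relative to the sampling SD. The shrinkage applies with or without status, however, so the omitting model still has the larger SE of the two.

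**The fewer-women column overstates the power loss.** It measures interval width only. Matched on power, the loss is 1 − (2.741/2.802)² = 4.3% at 0.5 SD and 1 − (2.651/2.802)² = 10.5% at 0.8 SD (50:50 split), where each numerator is 1.96 plus the normal quantile of the tabulated power. This stands as a reading of that column.

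**The harm is hypothetical and small.** No passage supports a difference as large as 0.8 SD, and at 0.2 SD power falls by 0.3 points. This stands, and it limits the weight of the point.

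**The readings are not certain.** Blocking within strata is the natural reading but is not spelled out. If elapsed months vary between women, group × time is not exactly a difference in mean change. With 15% random dropout, the ratio of reported to true SE at 1.0 SD is 1.09, against 1.11 with complete data.

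**Conclusion.** The concern holds. The blocking factor is missing from the main models for all six outcomes, and for five of them it appears in no model at all. For any outcome whose change differs between pregnant and postpartum women, the interval for group × time is wider than it need be and its test is conservative. The estimate is unbiased and the omission does not inflate false positives.

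The size is modest: about 3% on the standard error at a 0.5 SD difference, 6.5% to 7.7% at 0.8 SD, and nothing where change does not differ. These figures rest on blocks within strata, complete visits at common times, 5% alpha, 80% power and the assumed splits and differences. The change is worth making because it matches the analysis to the randomisation at almost no cost. It does not call the validity of the planned test into question.

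**What to change.** Add two fixed effects, perinatal status at randomisation and perinatal status × time, to the models for PHQ-9, DASS-21 Anxiety, DASS-21 Stress, BADS-SF, ATQ-SF and self-efficacy. The status × time term must be included, because it is the one that recovers the precision. Keep group × time × status in the PHQ-9 moderation model only, so that group × time in the main models remains a single average effect.

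The SAP is written in the past tense. If the analysis is complete, report the adjusted models as a labelled sensitivity analysis beside the planned ones.

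The cost is a sentence of SAP wording and two model terms on a variable already collected and used to randomise.

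### Maximum likelihood makes no deduction for the fixed effects, so, if within-woman correlation is modelled, the interaction standard errors are slightly too small; REML would remove this at almost no cost

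*Combined protocol and SAP*

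**What the plan says.** The Statistical Analysis Plan section describes the outcome models as "fixed effects growth models fit (SAS PROC MIXED; Version 9.4) and estimated with maximum likelihood". The predictors are a "two-level dummy coded group variable (coded 0 for PDP and 1 for MMB2+PDP"), together with "a time variable (coded in months elapsed between baseline and posttest), and a group \times time interaction". Under Measures and Assessments, "outcomes were assessed at baseline and the 12-week posttest", so each woman contributes at most two values per outcome.

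Moderators of the PHQ-9 effect "were evaluated by adding in separate models, the main effects of baseline perinatal status (pregnant/postpartum), the EPDS primary screen, baseline PHQ-9", with "all two- and three-way higher order interactions with group and time". Each moderator therefore has its own model.

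The section does not state a covariance structure for the two assessments, a degrees-of-freedom method, a small-sample correction, a significance level or a sample size. It also does not say whether the moderator terms are judged by single-coefficient tests or by likelihood-ratio comparison with the base model.

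**The concern.** ML estimates a variance by dividing by the number of units, with nothing taken off for the mean parameters fitted. REML makes that deduction. When the covariance model is otherwise right, ML standard errors are too small in finite samples, confidence intervals too narrow and p-values too small. The shortfall grows with the number of fixed effects, so it is larger in the moderation models than in the main model.

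The usual reason to prefer ML is that it permits likelihood-ratio comparison of models with different mean structures, and the plan names no such comparison. As written, it takes on the finite-sample bias of ML without saying what is gained. The same model serves both primary outcomes (PHQ-9 and DASS-21 anxiety), the secondary outcomes and the three PHQ-9 moderators, so any effect is repeated across all of them.

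**Working it through.** The plan gives no figure to reproduce: it states no sample size, significance level or power.

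**Inputs from the documents**
- Two groups and two assessments.
- Main model: four fixed effects (intercept, group, time, group by time). Two of them, time and group by time, describe the change from baseline, so p = 2.
- Each moderator model: eight fixed effects. Four of them describe change, so p = 4.

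**Assumptions**
- n, the number of women with both assessments, is 40, 100 or 200.
- Two-sided 5% level with a t reference distribution.
- Within-woman correlation is modelled (random intercept or unstructured 2x2 covariance).

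**Step 1: ratio of standard errors.** With complete data at two assessments, each interaction test is a regression of change with p parameters. ML uses the residual sum of squares divided by n; REML divides by n − p. Hence

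SE(ML) / SE(REML) = √((n − p)/n).

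- Group by time, n = 100: √(98/100) = 0.990, or 1.0% low.
- Three-way term, n = 100: √(96/100) = 0.980, or 2.0% low.

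**Step 2: true level.** With T following a t distribution on n − p degrees of freedom,

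true level = 2·P(T > t₀.₉₇₅ × √((n − p)/n)).

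- Group by time, n = 40: t₀.₉₇₅ on 38 df is 2.024; 2.024 × 0.9747 = 1.973; level 0.0558.
- Three-way term, n = 100: t₀.₉₇₅ on 96 df is 1.985; 1.985 × 0.9798 = 1.945; level 0.0547.

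| n | Group by time: SE low by | True level | Three-way: SE low by | True level |
|---|---|---|---|---|
| 40 | 2.5% | 5.6% | 5.1% | 6.2% |
| 100 | 1.0% | 5.2% | 2.0% | 5.5% |
| 200 | 0.5% | 5.1% | 1.0% | 5.2% |

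Under REML, in this complete-data setting, the level is exactly 5.0%.

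**Step 3: simulation with dropout.** ML and REML were fitted to the same simulated data with 1:1 groups, a compound-symmetric covariance, correlation 0.45, 20% missing posttests, varying elapsed months and 4,000 replicates (Monte Carlo standard error about 0.0035). All of these settings are assumptions. N is the number randomised.

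| N | Group by time, ML / REML | SE ratio | Three-way, ML / REML | SE ratio |
|---|---|---|---|---|
| 40 | 0.064 / 0.056 | 0.970 | 0.068 / 0.052 | 0.940 |
| 100 | 0.056 / 0.052 | 0.988 | 0.057 / 0.052 | 0.976 |
| 200 | 0.052 / 0.050 | 0.994 | 0.048 / 0.045 | 0.988 |

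ML rejects more often than REML in all six comparisons. The gap at N = 200 is 0.2 to 0.3 percentage points.

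**Step 4: what if the two assessments are treated as independent?** For group by time, with within-woman correlation ρ, the reported standard error relative to the correct one is √((2N − 4)/(2N)) / √(1 − ρ) under ML. At N = 100 the numerator is √(196/200) = 0.990.
- ρ = 0.2: 0.990/0.894 = 1.107. The standard error is 11% too large and the level is about 3.0%.
- ρ = 0.5: 0.990/0.707 = 1.400. The standard error is 40% too large and the level is about 0.6%.

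REML replaces the numerator by 1, giving 1.118 and 1.414, so the test is conservative under either method. An unmodelled correlation matters far more than the choice between ML and REML.

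**The case against.** A reader might infer that every interaction standard error in this trial is biased low and that the tests always lean toward a false positive. The documents do not support that. It requires the within-woman correlation to be modelled, and the plan states no covariance structure. If fixed effects growth models means models with neither a random effect nor a residual correlation, the group by time test is conservative even under ML. What holds more generally is the comparison: under the same covariance structure, ML omits a deduction that REML makes.

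A reader might also infer that the primary results are materially anticonservative. Nothing in the documents shows a small sample, and from n = 100 upward the analytic excess is about half a percentage point or less. Levels near or above 6% arise for the three-way terms only in samples well below 100.

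A third tempting reading is that Cohen's d is inflated. That would follow only if d were standardised by a model-based ML standard deviation, and the plan does not say which standard deviation is used.

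Finally, ML is a standard method and choosing it is not an error. It uses the available data under missing at random, as REML does, and it is the valid choice for likelihood-ratio tests of added fixed effects. The description of moderators being added to the model could mean such a test, so its absence cannot be taken as certain. This limits the recommendation without removing it: if such a test is intended, the plan should say so and use ML for that step only.

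**Conclusion.** The point holds as a minor improvement. If each woman's two assessments are modelled as correlated, ML makes the group by time and three-way standard errors slightly too small, by the amounts tabulated above, and the tests run slightly above 5%. The moderator terms carry about twice the shortfall of the main interaction. At n of 100 or more, conclusions would rarely change.

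The sizes rest on an assumed range of n, a two-sided 5% level, a t reference distribution and a modelled within-woman correlation; the documents state none of these. The covariance structure is the more consequential omission, because it decides whether the tests err above or below the nominal level.

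**What to change.** In the Statistical Analysis Plan section, replace the statement of ML estimation with wording such as: *estimated with restricted maximum likelihood and Kenward-Roger degrees of freedom, with the two assessments of each woman modelled as correlated (unstructured 2x2 covariance or a random intercept)*. Apply it to the primary, secondary and moderation models. If a likelihood-ratio comparison of nested mean models is intended for the moderation analyses, say so and keep ML for that comparison alone.

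The cost is one phrase in the plan, METHOD=REML and DDFM=KR in the PROC MIXED call, and an explicit RANDOM or REPEATED statement if there is none already. No data are lost: women without a posttest still contribute their baseline values under the same missing-at-random assumption.

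### The main model gives each randomised arm its own baseline mean, so with two visits group × time is essentially a change-score comparison, generally less precise than a baseline-adjusted analysis

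*Combined protocol and SAP*

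**What the plan says.** Women are randomised to two groups, with allocation "blocked on perinatal status (pregnant or postpartum) and the two groups" (Participant Recruitment, Enrollment, and Randomization). Under Measures and Assessments, "outcomes were assessed at baseline and the 12-week posttest", so each outcome has two values per woman.

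The Statistical Analysis Plan describes intent-to-treat "fixed effects growth models fit (SAS PROC MIXED; Version 9.4) and estimated with maximum likelihood". The outcome from baseline to posttest is "predicted by a two-level dummy coded group variable (coded 0 for PDP and 1 for MMB2+PDP), a time variable" in elapsed months, plus group × time. Baseline is thus one of the two responses, not a covariate. The within-person covariance structure is not stated.

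Baseline score and the blocking factor appear only in the moderation analysis, which is limited to PHQ-9 and is "evaluated by adding in separate models, the main effects of baseline perinatal status (pregnant/postpartum), the EPDS primary screen, baseline PHQ-9", with their interactions with group and time. DASS-21 Anxiety, the other primary outcome, has no baseline adjustment anywhere, and neither do the secondary outcomes.

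**The concern.** With time counted from baseline (an inference from the coding described, but the natural one), the group coefficient is the arm difference at baseline. Randomisation makes its expected value zero, yet the model estimates it freely. With only two visits, the interaction then reduces to the difference between arms in mean change. Subtracting the whole baseline score is the best use of it only when the slope of posttest on baseline is 1. Otherwise part of the baseline noise is carried into the treatment contrast.

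This is the only group test described for both primary outcomes (PHQ-9 and DASS-21 Anxiety) and for all secondary outcomes. The baseline scores that would recover the lost precision are already collected.

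**Working it through.** **Inputs.** From the documents: two randomised arms, two visits, and a model with group, time and group × time. The documents give no sample size, alpha, power, effect size, SD, correlation or dropout, so there is no planned figure to reproduce. The following are assumed:

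- r, the baseline–posttest correlation: 0.3, 0.5 or 0.7
- k = SD baseline / SD posttest: 1, 0.8 or 0.7. Values below 1 are plausible because recruitment required an EPDS score above 12, which may compress baseline spread.
- p, the proportion with a posttest: 1 or 0.8, missing completely at random
- for the power figures only: two-sided alpha 0.05 and 80% power for the common-baseline model, so that effect / SE = 1.96 + 0.84 = 2.80

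**Step 1: is the interaction a change-score contrast?** In one simulated two-visit data set (60 per arm, r = 0.5, complete data, common timing), a maximum-likelihood fit of the planned fixed effects with a random intercept gave interaction × elapsed months = −0.1138. The difference in mean change was also −0.1138. The SE was 0.189, against 0.161 for ANCOVA on the same data. With elapsed time varying between women and no missing data, the interaction correlated 0.997 to 0.998 with the simple change contrast. With 15% of posttests missing the correlation was 0.97 to 0.99. The identity is exact in the simple case and close otherwise.

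**Step 2: variances, in posttest-variance units, complete data.**

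- Change: 1 − 2rk + k²
- Baseline-adjusted (common baseline): 1 − r²
- Difference: (k − r)², which is never negative and is zero only at k = r

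With posttests missing, the planned contrast has variance proportional to (1 − r²)/p + (k − r)² and the common-baseline contrast (1 − r²)/p. The ratio is

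R = 1 + p(k − r)²/(1 − r²).

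Example: k = 1, p = 1, r = 0.5 gives 1 + 0.25/0.75 = 1.33.

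**Step 3: power of the planned contrast** = Φ(2.80/√R − 1.96). Example: 2.80/√1.333 = 2.425, and Φ(0.465) = 68%.

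| Setting | R at r = 0.3 / 0.5 / 0.7 | Power at r = 0.3 / 0.5 / 0.7 |
|---|---|---|
| k = 1, p = 1 | 1.54 / 1.33 / 1.18 | 62 / 68 / 73% |
| k = 1, p = 0.8 | 1.43 / 1.27 / 1.14 | 65 / 70 / 75% |
| k = 0.8, p = 1 | 1.27 / 1.12 / 1.02 | 70 / 75 / 79% |
| k = 0.7, p = 1 | 1.18 / 1.05 / 1.00 | 73 / 78 / 80% |

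In the first row the SE is √R = 1.24, 1.15 and 1.08 times as large, and the same power needs 54, 33 and 18% more women.

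**Step 4: simulation check** (100 per arm, 8,000 trials per cell). The ratios at r = 0.3 / 0.5 / 0.7 were 1.53 / 1.32 / 1.17 for k = 1, p = 1; 1.44 / 1.27 / 1.13 for k = 1, p = 0.8; and 1.27 / 1.12 / 1.01 for k = 0.8, p = 1. Both contrasts averaged within 0.003 SD of the true zero effect, so neither is biased.

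**Outside the tabled range.** If baseline spread exceeds posttest spread the loss is larger. At k = 1.25 with complete data, R = 1 + 0.95²/0.91 = 1.99, 1 + 0.75²/0.75 = 1.75 and 1 + 0.55²/0.51 = 1.59.

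**The case against.** The strongest reply is that this is an efficiency preference. A group × time growth model is standard and interpretable, uses actual elapsed time, and under maximum likelihood can keep women who lack a posttest. That is correct, and the point makes no claim of bias.

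Second, the starting power of 80% is not in the documents and is assigned here to the common-baseline model. If the trial was sized for the planned contrast, that test has its intended power and adjustment is a bonus: with equal SDs and complete data, Φ(2.80√R − 1.96) gives about 93, 90 and 86%. This stands. The power figures are illustrative; the variance ratios do not depend on them.

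Third, the loss may be negligible. At k = 0.8 with r of 0.5 to 0.7 it is 1 to 5 power points, and at k = 0.7 it is 0 to 2. This also stands, but the large-sample variance of the adjusted analysis is never higher.

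Fourth, no gain has been quantified for perinatal status, and a stable difference between pregnant and postpartum women cancels from a change contrast. Including it rests on its role as the blocking factor.

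Fifth, the unstated covariance may matter more. If no within-person correlation is modelled, the point estimate with complete data and common timing is unchanged but its SE is wrong. That limits the statement that only precision is at issue, and it is why the fix must name a structure.

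**Conclusion.** The concern holds. The planned group × time test is essentially a change-score comparison, and in expectation it is never more precise than a common-baseline analysis of the same data. Over the assumed range (r from 0.3 to 0.7, k from 0.7 to 1, up to 20% of posttests missing completely at random), its variance is 1.00 to 1.54 times as large. The illustrative loss runs from zero, when k = r, to about 18 power points, and it is larger if posttest spread is smaller than baseline spread. The actual size cannot be determined from the documents. With within-person covariance modelled, the planned contrast is unbiased under randomisation, so this is an improvement the plan should make and not an error that invalidates the analysis.

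**What to change.** For both primary and all secondary outcomes, specify a common-baseline longitudinal model:

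- terms for visit and for treatment at the 12-week posttest, with no group main effect
- perinatal status and perinatal status × visit as covariates
- an unstructured within-person covariance (REPEATED / TYPE=UN)
- all randomised women kept in the model

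State that the estimand becomes the difference at the 12-week posttest and is no longer a difference in monthly slopes. Keep the elapsed-months model as a sensitivity analysis, with its covariance structure stated.

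A smaller change would also remove the inefficiency: drop the group main effect, keep time and group × time in elapsed months, and state the covariance. This retains the slope estimand. ANCOVA of posttest on group, baseline score and perinatal status is simpler still, but it uses only women with a posttest and should not be described as keeping all randomised women.

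The cost is SAP wording and a few SAS statements, with no new data. The plan is written in the past tense and the research team was unblinded after randomisation. If results already exist, report the new model beside the planned one and label it post hoc; it should not replace the planned analysis.

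### Does coding time in months elapsed bias the group × time test, or make the stated Cohen's d wrong?

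*Combined protocol and SAP*

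**What the plan says.** Under Measures and Assessments, "outcomes were assessed at baseline and the 12-week posttest", so each woman has at most one post-baseline value. The Statistical Analysis Plan states: "Intent-to-treat analyses of group effects were performed using fixed effects growth models fit (SAS PROC MIXED; Version 9.4) and estimated with maximum likelihood". Treatment arm enters the model as a "two-level dummy coded group variable (coded 0 for PDP and 1 for MMB2+PDP"). The second predictor is "a time variable (coded in months elapsed between baseline and posttest"), and the third is the product of these two. The effect sizes for the group × time "interaction are equivalent to Cohen's d".

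The plan does not say whether months are each woman's actual interval or a nominal value, though the wording reads more naturally as actual. It gives no posttest window, no standardising SD and no formula for d. It also states no sample size or expected effect, so there is no figure of its own to reproduce.

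**The concern.** Two things look wrong.

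The first is scale. With time in months and group coded 0/1, the interaction is a difference in monthly slopes. It is not the 12-week difference, and dividing it by an SD does not give Cohen's d. A reader who took slope/SD for d would understate the effect by a factor of 2.76.

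The second is bias. With one follow-up, the model makes change proportional to how late a woman answers. If improvement has stopped by 12 weeks, a late answer flattens her slope. Elapsed time arises after randomisation and could differ by arm. The team is unblinded, and outreach is described only for MMB2+PDP: "Call #1, 2-4 weeks following randomization, focused on resolving any difficulties signing into MMB2". Levelling off is plausible because "each of the six MMB2 sessions becomes available sequentially according to a weekly schedule", so all content is open about halfway through the 12-week active phase. Improvement common to both arms could then appear as a group effect or hide a real one, on both primary outcomes (PHQ-9 and DASS-21 Anxiety).

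**Working it through.** **Inputs.** From the documents: two assessments, 12 weeks apart, and time in months. Assumed, because the documents give no values: SD 5, baseline–posttest correlation 0.5, 200 women, a 5-point improvement in both arms, and posttest at 12 weeks plus an exponential delay.

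**Scale.** T = 84 / 30.44 = 2.76 months. If D is the 12-week difference, the coefficient is b = D/T, so D = b × T and d = b × T / SD. For D = 2.0 and SD 5:

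- b = 2.0 / 2.76 = 0.72 points per month
- b / SD = 0.145
- b × T / SD = 0.40, the correct d

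A d derived from the t statistic does not depend on time units. It equals d × 1/√(2(1 − r)), that is 0.85, 1.00 or 1.29 times d at r = 0.3, 0.5 or 0.7.

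**Timing, by hand.** Let the MMB2+PDP arm answer 2 weeks later, with no true effect.

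- Change levelled off: the slopes are −5/2.76 = −1.81 and −5/3.22 = −1.55. Their difference is 0.259 per month, or +0.71 points over 12 weeks. Visit coding gives 0.
- Change linear: both slopes are −1.81, so the planned coding gives 0. Visit coding gives −5 × 2/12 = −0.83.

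**Timing, by simulation** (random delays, 4,000 replicates per scenario). Entries are points at 12 weeks; negative favours MMB2+PDP. Percentages are false rejection when the truth is 0 and power when it is −2.0.

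| Change | Truth | Mean delay in months, PDP / MMB2+PDP | Months elapsed × 2.76 | Visit coding |
|---|---|---|---|---|
| levelled off | 0 | 0.3 / 0.6 | +0.51 (14%) | about 0 (5–6%) |
| levelled off | 0 | 0.3 / 0.8 | +0.81 (29%) | about 0 (5–6%) |
| levelled off | −2.0 | 0.3 / 0.6 | −1.06 (42%) | about −2.0 (81%) |
| linear | 0 | 0.3 / 0.6 | about 0 (5%) | −0.52 (12%) |
| linear | 0 | 0.3 / 0.8 | about 0 (5%) | −0.92 (26%) |
| linear | −2.0 | 0.3 / 0.6 | −1.99 | −2.97 |

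The visit-coding results under linear change agree with hand arithmetic: 0.3 × 5/2.76 = 0.54, 0.5 × 5/2.76 = 0.91, and 3.36 × 7/2.76 − 3.06 × 5/2.76 = 2.98.

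**Remaining cases.** If change has levelled off, reversing the delays to 0.6 / 0.3 turns the bias to −0.52. Equal delays of 0.3 or 0.6 months shrink a true −2.0 to −1.78 or −1.58. When both arms average 12 weeks, the two codings agree: for a true −2.5, with 150 per arm and 60 replicates, they gave −2.46 and −2.47 (linear) and −2.64 and −2.67 (levelled off). If months are one nominal value for everyone, recoding to 0/1 only rescales the coefficient and leaves the test statistic unchanged.

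**The case for a change.** The best case for a change is that linearity cannot be checked from two points per woman, that sessions open weekly and are all available by mid-phase, and that even equal lateness attenuates the 12-week estimate if change has levelled off. Two analysts could also report different values of d from the same data. Visit coding would estimate the difference at the posttest directly, for the price of one recoded variable.

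Much of this is correct as arithmetic. The plan does leave d unspecified, and the results under levelled-off change hold on their assumptions. What does not stand is that visit coding is safer. Being unable to check linearity equally means being unable to establish levelling off. The session schedule says little about when mood stops improving, and nothing about the PDP arm, whose improvement also feeds the spurious effect. MMB2 also has a 12-week active phase, with access for 7 months afterwards.

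The route to unequal timing is weak too. The first call concerns sign-in and falls at 2–4 weeks; the second follows the posttest and cannot delay it. Assessments run online through REDCap with no arm difference described, and extra contact could prompt earlier answers as easily as later ones.

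**Conclusion.** The concern does not call for a change. On scale, the text refers to effect sizes for the interaction, not to the raw coefficient, and nothing says slope/SD will be reported. An analyst converts with the known factor of 2.76 and a baseline SD, and should state that formula with the result. This is a gap filled by ordinary practice.

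On bias, the choice is a fair trade-off. A shift of about 0.5 to 0.8 points against the planned coding (0.3 versus 0.6 or 0.8 months' mean delay) requires actual individual times, later answers in one arm, and change that has levelled off. Under linear change the same delays put visit coding off by about 0.5 to 0.9 points the other way, while the planned coding is correct. The documents settle neither the shape of change nor whether timing differs. All these sizes rest on an assumed SD of 5, a 5-point change, 200 women and the chosen delays. Reporting posttest timing by arm, with visit coding as a sensitivity analysis, would help readers judge the result, but the planned primary model can stand.
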